## **Objectives:**

1. To describe what type of information patients' want, need and prefer when having a dental check-up and how they use this information.

2. To describe how patients' interact with three different forms of information

3. To investigate whether and how the clinician/patient relationship is influenced by patients having access to different types of information

4. To measure individuals' preferences, by using the economic preference based valuation methodology Willingness to Pay for each of the three different methods of giving information.

5. To identify differences in preference for different types of information by differing demographic, behavioural and psychographic groups.

6. To use variables from derived established models of the behavioural change process to predict the likelihood that different forms of communication will lead to behaviour change; and to measure any actual behaviour change and link these with differences in valuations

7. To conduct a cost-benefit framework analysis of the three different methods and to explore financial implications for NHS dentistry.

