# Data analysis

Data sources from interviews, observations and ethnographic work will be integrated into a single analysis. Qualitative data analysis will adopt the principles of grounded theory which include a 'constant comparison' method, where interview texts are analysed line by line, provisional themes noted, and are subsequently compared with other transcripts in order to ensure consistency and to identify negative cases (Walker & Florence, 2006). Literature will be consulted as part of an iterative, inductive and interactional process of data collection, simultaneous analysis and emergent interpretation. Conceptual memos will be written alongside coding to document the development of codes, how codes are related to each other, and to existing theory in the area. Emerging perceptions from both the inductive and aggregate coding will be shared at 'data clinics' where project researchers meet to discuss and test emerging themes. Emerging concepts will be further probed and refined in interviews with the next participants to ensure validity of the data or to reject concepts which do not hold to further scrutiny. We will also involve members of the Research Advisory Group and some of the research participants to check the validity of our perceptions. A diary of thoughts and observations will be kept throughout the study and meetings with people involved in the analysis and interpretation of qualitative data, to provide opportunities to be reflexive about how researchers and the process of conducting research has influenced data collection and analysis. The software package NVIVO Version 10.0 will be used to aid indexing and retrieval, analysis and presentation of coding themes.

c) Preparation for Phase 2

# Overview of Phase 2

Phase 2 consists of an experimental design using randomisation at the patient level, of different forms of information (verbal information only, traffic light information QLF information) This will take place in four NHS dental practices (two in Salford, and two in Newcastle). We will collect patients' Willingness-To-Pay (WTP) for each of these types of information, as well as data on their perceived risk of dental disease and intended and actual behaviour change. Using clinical data (BPE scores measuring gingival health) and data on tooth mineral loss as well as plaque coverage measured from successive QLF photographs, we will also gather information on actual changes in oral health behaviours.

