credit-card sized information showing their risk level according to colour on the card. In the Verbal only arm patients will receive a plain card with a checklist where the message given by the dentist is written. The reverse of the credit-card sized information from the QLF arm and the Traffic Light arms will have the same checklist (Figure 1):

Figure 1: Checklist of possible preventive messages given to patients

- Stopping or quitting smoking
- Following your dental treatment plan

Following the check-up the dentist or nurse will record as data variables:

- The number of natural teeth present
- Whether the patient is exempt or not from NHS charges
- Any messages given as checked against the Figure 1 list
- The Red, Amber or Green risk rating assigned to patients in the Traffic Light arm

Following the dental appointment, all patients will be given the opportunity to revise their WTP for the information form experienced (therefore this will not be relevant to those in Model 1 who receive only verbal information and they will not undertake this part of the study). For this re-valuation, patients will be reminded of their initial valuation and then asked in a single open-ended question format if they wish to change the value and what amount they would change to.

Self-report data will then be collected at this point on:

- Intention to behave according to the behaviours listed in Figure 1 before the next appointment
- Behaviour change variables as outlined by the Extended Parallel Process Model (EPPM) (Severity of Threat, Susceptibility of Threat, Self-Efficacy and Response Efficacy). The 'threat' here will be the threat of poor oral health and its consequences identified from Phase 1 (for detail see Measures: 5b Risk (threat) perception). An additional set of items will be added to reflect affect concerned with negative oral health outcomes i.e. '*How would you feel if...*' (in addition to the cognition set reflected in EPPM domains).
- Patient-Clinician communication (Communication Assessment Tool, CAT).

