## Behaviour change and mediating variables

Plaque coverage provides an objective measure of tooth cleaning behaviour in the 48 hours preceding the measurement (because QLF images capture the maturity of the plaque), although it is not known whether consistent toothbrushing can be inferred. Plaque scores derived from the QLF analysis will be compared to the self-reported toothcleaning behaviour to assess the correlation between the two methods.

Differential reported behaviour change between the conditions will be assessed by creating a change score from one observation to the next by subtracting baseline scores from followup scores and conducting an analysis of mean differences using the baseline score as a covariate (Weinstein, 2007). Unless abnormally distributed, tooth cleaning behaviour will be treated as a continuum. Predicting oral health behaviours will involve the use of EPPM variables assessed during V1, and partly at V2 to predict later behavioural change.

The intervention is performed at the first visit. Thus, the change in EPPM scores (susceptibility to risk) from V1 to V2 will be used as the primary predictor variable. This will be used to predict changes in oral health behaviour from V2 to V3. We shall also use V1-V2 change scores to predict oral health behaviour changes from V2 to 6-month and 12-month (telephone) follow-ups. Structural equation models will be developed to represent these predictions, testing the predicted model as the model of best fit. Full information maximum likelihood methods (FIML) will be used to account for missing data (Muthén & Muthén, 1998–2010). With sample sizes greater than 250 participants, TLI, RMSEA, and SRMR are recommended. A TLI of .95, RMSEA of .06, and SRMR of .09 are recommended as cutoff values to accept the model as a good fit (Hu & Bentler, 1999).

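### The structural equation models name no term for randomised arm and no stated analysis compares arms on EPPM scores, so they cannot show whether a form of information acts through risk perception

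*Protocol*

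**What the plan says.** Objective 6 is, in part, to use variables from models of behaviour change to "predict the likelihood that different forms of communication will lead to behaviour change". The overview of Phase 2 makes form of information the randomised factor: "Phase 2 consists of an experimental design using randomisation at the patient level, of different forms of information".

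The Phase 2 analysis section on behaviour change and mediating variables then fixes:

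- **Predictor:** "the change in EPPM scores (susceptibility to risk) from V1 to V2 will be used as the primary predictor variable". The section also says more generally that EPPM variables from V1, and some from V2, will be used.
- **Outcome:** "This will be used to predict changes in oral health behaviour from V2 to V3", and likewise from V2 to the 6-month and 12-month telephone follow-ups.
- **Model:** "Structural equation models will be developed to represent these predictions, testing the predicted model as the model of best fit".
- **Missing data and fit:** full information maximum likelihood, with cut-offs for TLI (.95), RMSEA (.06) and SRMR (.09).

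Arm enters two other analyses. In the same section, "Differential reported behaviour change between the conditions will be assessed by creating a change score from one observation to the next", with the baseline score as covariate. In the section comparing clinical outcomes, QLF measures are compared between the three groups in a repeated measures mixed model.

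On timing, the Visit 1 procedures place EPPM collection after the dental appointment at which the randomised information is given: "Self-report data will then be collected at this point on", followed by a list that includes the EPPM variables. At Visit 2 only the susceptibility items are repeated.

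**The concern.** The objective is about forms of communication, and both the analysis heading and item 5 of Measures describe the EPPM variables as mediators. A mediator stands between an exposure and an outcome. The stated models have a mediator and an outcome, but the exposure, which is the one randomised factor in Phase 2, is not named.

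Two quantities are therefore not estimated by any stated analysis:

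- the effect of each form of information on perceived threat, efficacy, fear, intention, or danger and fear control; and
- the part of any behaviour effect that runs through those variables.

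The risk is one of interpretation. A model that meets all three fit cut-offs could be reported as evidence about how Traffic Light or QLF information works. It would show only that patients whose perceived susceptibility rises also tend to change behaviour more.

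**Working it through.** **1. Stated analyses side by side**

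| Link | Stated analysis | Randomised comparison? |
|---|---|---|
| Arm to reported behaviour | Change scores between conditions, baseline as covariate | Yes (total effect) |
| Arm to QLF outcomes | Repeated measures mixed model | Yes (total effect) |
| Arm to EPPM variables | None stated | – |
| EPPM to later behaviour | Structural equation models | No |
| Arm to behaviour through EPPM | None stated | – |

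**2. The plan's own calculation**

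The only calculation in the protocol is for plaque percent index: 133 per group, SD 10, difference 3.5, 80% power, alpha 0.05 (two-sided assumed). The detectable difference is 10 × √(2/133) × (1.960 + 0.842) = 3.44, and power for 3.5 is 81.4%. The figure is sound and the point does not depend on it. On the same basis, a pairwise comparison of any EPPM score at 133 per arm has 80% power for 0.344 SD. The randomised contrast that is not stated would therefore be informative.

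**3. What the EPPM-to-behaviour path tells us about arm**

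Illustrative simulation with all effect sizes assumed: 3 × 133 patients, 2,000 runs. Stable susceptibility has SD 1 and each measurement adds error of SD 0.5. The slope of behaviour change on EPPM change is 0.3, and the QLF arm shifts susceptibility by a. Behaviour change is regressed on EPPM change with no arm term.

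| a (SD) | Path significant (V1 EPPM before / after information) | Mean slope |
|---|---|---|
| 0 | 99.2% / 98.3% | 0.30 / 0.30 |
| 0.3 | 98.7% / 98.2% | 0.30 / 0.30 |
| 0.5 | 99.4% / 98.9% | 0.30 / 0.30 |

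The result is the same whether or not the arm moves perceived risk.

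**4. Why adding arm to the stated predictor is not enough**

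Let B be a patient's underlying susceptibility, a the effect of the information, and e1 and e2 measurement error. Because V1 EPPM follows the information:

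- V1 = B + a + e1
- V2 = B + a + e2, if the effect persists
- V2 − V1 = e2 − e1, so a cancels.

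If only a fraction r of the effect remains at V2, the arm contrast in the change is −(1 − r)a. That measures fading, not the effect of the information.

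In the same simulation, an arm-to-change path is detected as follows:

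| a (SD) | If V1 EPPM preceded the information | V1 EPPM after the information, as in the protocol |
|---|---|---|
| 0 | 5.2% | 5.5% |
| 0.3 | 93.8% | 5.5% |
| 0.5 | 100% | 5.3% |

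Under the protocol's timing, detection stays at the false-positive rate whatever the true effect.

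**5. Can leaving out arm create a spurious path?**

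Suppose there is no true EPPM-to-behaviour path, QLF shifts both change scores by d SD and Traffic Light by d/2. The between-arm covariance is d²/6, so the induced correlation is (d²/6)/(1 + d²/6). At d = 0.5 this is 0.0417/1.0417 = 0.040. Multiplied by √399 it gives 0.80, and a rejection rate of about 12.6%. Simulation (4,000 runs) gave 5.8%, 8.6%, 12.9% and 20.6% at d = 0.3, 0.4, 0.5 and 0.6, and about 5% with arm in the model. If arm does not shift the V1 to V2 change, which step 4 shows is plausible, the rate is 4.8–5.2% at every d from 0.2 to 0.6.

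**The case against.** **Silence is not exclusion.** A reader might infer that all patients are pooled and that arm is left out by design. The text says neither. The remark "With sample sizes greater than 250 participants, TLI, RMSEA, and SRMR are recommended" argues against separate models for arms of 133, but it fits a multi-group or arm-adjusted model on about 400. A statistical analysis plan, not shown here, could add the arm paths. This stands, so the point is limited to what the stated models name. It does not dispose of the point: the protocol itself fixes the primary predictor, outcomes, model class, missing-data method and fit criteria, and these together leave arm without a role.

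**The change score is not the only predictor.** Calling it primary, and referring to EPPM variables from V1, implies others. This also stands, but those others are EPPM variables, not arm.

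**No indirect-effect test is promised.** Objective 6 speaks of predicting, not of effects through the EPPM variables, and it also covers links with valuations. That is correct, and it would be too strong to say that a promised mediation test is missing. The mediation language is the protocol's own, though, and the objective's subject is the form of communication.

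**The randomisation is used for behaviour.** It is, in two stated analyses. It would be wrong to say that the plan cannot compare the forms of information on behaviour. What it lacks is the arm-to-EPPM link and the indirect effect.

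**Conclusion.** The point holds in limited form. As written, the structural equation models can show only a non-randomised association between EPPM change and later behaviour change. They do not address whether Verbal, Traffic Light and QLF information differ in their effect on perceived risk, or whether such a difference carries through to behaviour.

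This is a gap in model structure; no stated figure changes. The simulated percentages rest on assumed effect sizes and serve only to illustrate it. A reader might infer that omitting arm seriously inflates false positives. The documents do not support that: rates of 12.9–20.6% need arm shifts of 0.5–0.6 SD in both change scores, inflation is negligible at 0.3 SD or less, and there is none if arm does not shift the V1 to V2 change.

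The primary outcome, willingness to pay, is unaffected. The change is worth making because the objective and heading invite a conclusion that the stated models cannot deliver, and the data needed are already to be collected.

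**What to change.** In the section on behaviour change and mediating variables:

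1. Add two arm indicators (Traffic Light and QLF, each versus Verbal) as exogenous variables in the structural equation models.
2. Give them paths to the V1 EPPM scores collected after the information. These are comparable between arms by randomisation, so no pre-information EPPM score is needed for the contrast.
3. Give them direct paths to behaviour change. Take behaviour change from the pre-information V1 baseline as well as from V2, because change completed by V2 is lost from a V2 to V3 difference. Self-reported behaviours and QLF photographs are both collected at V1 before the check-up.
4. Report the arm-to-EPPM contrasts, and the direct and indirect effects with bootstrap intervals.
5. Describe the EPPM-to-behaviour path as observational.
6. If the V1 to V2 susceptibility change stays as a predictor, state that it excludes any effect of the information already present at V1.

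Cost: analysis wording and a few more model parameters. Arm is known for every patient, and no new data are needed.

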## Comparing clinical outcomes between the three intervention arms

Comparison of QLF outcomes between the three groups will use a repeated measures mixed model approach. These models allow for analysis of multiple measurements within each participant. In this case each QLF outcome will be measured at three time-points. The first time-point is the baseline measurement, and the measurement taken here will be used as a covariate in the final model. The repeated measures approach allows us to analyse both follow-up measures (V2 and V3) together, while adjusting for the correlation of repeated measurements within participants. Using a mixed model approach, rather than a repeated measures ANOVA, allows for flexibility in the event of missing data, and can adjust for multiple covariates in the model. If there is a high level of missing data, a multiple imputation approach will be used to assess the robustness of the results. Using all the data which is available, 5 complete case data sets will be imputed, and each analysed in the same way. The results can then be combined, and compared with the analysis excluding missing data, to assess whether this would be likely to change the overall conclusions.

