#### **Participants**

The study will involve 400 adult patients (aged 18 years or older), (100 in each of the four dental practices), who have been identified clinically as having high/medium oral health need/ risk of disease. We will use the nationally developed algorithm categorising patients as Red/Amber to define patients who are eligible for inclusion in the study. We will include patients will low literacy, but exclude patients who require an interpreter for dental care.

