# **Randomisation**

After patients are recruited to the study, a trained nurse in each practice will the randomise patients to one of three study arms (Verbal information only (n=133); Traffic Light Information (n=133); QLF information (n=133). This will be done using a randomisation schedule for each practice, drawn up by the statistician ([name]); allocating patients using sequentially numbered envelopes. The envelope will be opened by the dentist at the check-up and procedure followed according to which study arm the patient has been allocated to.

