Patient-Clinician communication (Communication Assessment Tool, CAT). This 15 item tool is designed to test the interpersonal and communication skills of clinicians (Makoul, Krupat and Chang, 2007). It has been applied in a range of settings including dentistry (Waylen, Makoul and Albeyatti, 2015), where 'doctor' is replaced by 'dentist'. A five point Likert scale is used (1=poor, 2=fair, 3=good, 4=very good, 5=excellent).

Individual clinician code for the appointment (V1, V2, V3)

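### Patients are randomised within practice, but the two between-arm models for secondary outcomes name only the baseline value; adding practice would gain a little precision at no cost

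*Protocol*

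**What the plan says.** **Allocation.** The overview of Phase 2 puts the unit of randomisation at the individual: "Phase 2 consists of an experimental design using randomisation at the patient level". The Randomisation section adds: "This will be done using a randomisation schedule for each practice". Recruitment is fixed at "100 in each of the four dental practices", with three arms of 133. The dentist opens the envelope and delivers the allocated information, so each dentist can be expected to deliver all three formats.

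**Analysis.** For QLF outcomes, the section on comparing clinical outcomes specifies a repeated-measures mixed model of V2 and V3. Of the baseline it says: "the measurement taken here will be used as a covariate in the final model". The only correlation it mentions is that between repeated measurements on one participant. It notes that such a model can accommodate several covariates but lists no others. For reported behaviour, the protocol plans change scores, "conducting an analysis of mean differences using the baseline score as a covariate". Practice and clinician appear in neither.

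**Data available.** Section 1(b) of Measures, on dentists' characteristics, records a clinician code at V1, V2 and V3. The same subsection holds the Communication Assessment Tool (CAT): "This 15 item tool is designed to test the interpersonal and communication skills of clinicians". The Visit 1 procedures show that patients complete the CAT after they have received the allocated information.

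**The concern.** A factor that restricts the randomisation normally belongs in the model. Four practices in two cities may well differ in patients' plaque levels and habits. When arms are balanced within practice, those differences cancel from the arm contrast. A model without practice still counts them as residual noise, so it reports less precision than the design delivers.

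The clinician raises a separate question. The format is delivered by a dentist, and if some dentists deliver one format better than another, patients of one dentist share part of the arm effect. The planned models would not see that.

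Finally, the CAT is classed with explanatory variables although it is measured after the intervention. Objective 3 asks whether the type of information influences the clinician-patient relationship, and the CAT is a measure of that. Used as an adjustment covariate, it could absorb part of an arm effect.

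**Working it through.** **Inputs from the protocol (sample size section).** SD of the plaque percent index (PPI) 10; 133 per arm; difference 3.5; 80% power; 0.05 level, taken here as two-sided. The protocol gives no practice or clinician variance, so those below are assumptions.

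**Step 1: the plan's own figure.** SE of an arm contrast = 10 × √(2/133) = 1.226. Power for 3.5: 3.5/1.226 = 2.854; 2.854 − 1.960 = 0.894; power 81.4%. Difference detectable with 80% power: 1.226 × (1.960 + 0.842) = 3.44. The stated figures are sound.

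**Step 2: leaving practice out, allocation balanced within practice.** Let *r* be the share of residual variance due to practice. The unadjusted model reports an SE that is 1/√(1 − *r*) times the correct one. Its true type I error is 2 × [1 − Φ(1.960/√(1 − *r*))]. With practice in the model, the SD becomes 10 × √(1 − *r*).

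| *r* (assumed) | SE overstated by | True type I error, practice omitted | Power with practice | Detectable difference with practice |
|---|---|---|---|---|
| 0.01 | 0.5% | 0.049 | 81.8% | 3.42 |
| 0.05 | 2.6% | 0.044 | 83.4% | 3.35 |
| 0.10 | 5.4% | 0.039 | 85.3% | 3.26 |

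Put another way, the unadjusted model reports the precision of a trial smaller by the fraction *r*: 4, 20 or 40 of 400 patients.

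**Step 3: simulation.** 4,000 replicates per setting, 4 practices of 100, 3 dentists per practice (assumed), arms balanced within practice, no true arm effect. With practice omitted, type I error was 0.046, 0.0485 and 0.0375 for practice shares of 0.02, 0.05 and 0.10. The Monte Carlo error is about √(0.05 × 0.95/4000) = 0.003. With practice and dentist shares of 0.05 each, it was 0.047. At a share of 0.10 the actual spread of the estimate was nearly the same with or without practice (1.152 and 1.154), while the mean reported SE was 1.161 with it and 1.208 without. That overstatement (1.208/1.161 = 1.041) is a little below the formula's because only four practice effects are drawn, so their realised share averages less than *r*.

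**Step 4: when would standard errors be too small?** Only if the arm effect itself varies by dentist. With practice and dentist shares of 0.05 each, a dentist-by-arm share of 0.02 gave type I error 0.063, and a share of 0.05 gave 0.107. Adding practice does not cure this (0.072 and 0.118). In closed form, with delivery SD *s* in each arm and *J* clinicians, SE = √(100 × 2/133 + 2*s*²/*J*):

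- *s* = 1, *J* = 12: √(1.504 + 0.167) = 1.292, or 5% above 1.226.
- *s* = 2, *J* = 8: √(1.504 + 1.000) = 1.582, or 29% above.

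The second case is demanding. It implies that the arm difference varies between clinicians with SD 2 × √2 = 2.8 PPI points, against a target difference of 3.5.

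**The case against.** **The covariate list is open.** The mixed model may take more covariates, the clinician code is collected, and a full list is commonly left to the statistical analysis plan, which is not shown. This stands: the protocol names only the baseline, but it does not restrict adjustment to the baseline. What remains is that it fixes the core of both models without its own randomisation stratum.

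**Balance within practice is inferred.** A schedule per practice is stated; blocking is not. Under simple randomisation within practice the unadjusted standard error would be valid, and adjustment would only add efficiency. This stands, and it is why the result is conditional.

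**Baseline adjustment already does some of the work.** Stable practice differences in plaque would partly pass through the baseline value. The SE of 1.226 also ignores the baseline covariate and the joint use of V2 and V3. The percentages are therefore indicative.

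**Stronger readings that the protocol does not support.** A reader might infer that the planned standard errors are too small and invite false positives, as in a cluster trial. Patients are randomised individually and dentists deliver all arms, so omitting practice and clinician main effects errs the other way. A shortfall needs variation of the arm effect between clinicians, which is plausible but unquantified here. A reader might also infer that the plan adjusts for the CAT, or for the failed-appointment count that accrues during the study. Both are classed as explanatory variables, but no section enters either into an arm comparison, so that harm is hypothetical.

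**Conclusion.** The point holds as a modest improvement to two secondary analyses. Given balance within practice, omitting practice overstates standard errors by about 0.5% to 5.4% for assumed practice shares of 1% to 10%. At most this gives up about four points of power (81.4% against 85.3%). The 133 per arm remains adequate for the stated PPI difference, and type I error stays at or below its nominal level unless the arm effect varies by clinician. On that question the protocol offers no figure, so it merits a sensitivity analysis and does not establish an error. The classification of the CAT should be corrected because of when it is measured. The primary hypothetical willingness to pay is elicited from every patient, for both systems, before the envelope is opened, so it is largely unaffected.

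**What to change.** 1. State that the QLF mixed model and the behaviour-change analysis of covariance include practice as a fixed effect alongside the baseline value. This uses three degrees of freedom.
2. As a sensitivity analysis, use the V1 clinician code to add random effects for clinician and, if estimable, clinician by arm. Report how far the standard errors of the arm contrasts move. With few clinicians the interaction variance may be poorly estimated, which is why this should not be the main model.
3. State that the CAT is analysed as an outcome across the three arms and is not an adjustment covariate in arm comparisons.

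Practice is known for every patient, and the clinician code and CAT are already collected. The cost is a few sentences of model specification and one extra sensitivity analysis, with no new data and no change in sample size.
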